#### **Secondary Outcomes**

As far tendon thickness and isometric strength of elbow flexors and extensors the difference in mean change from baseline to 6 and 12 weeks and the corresponding 95 % confidence interval (CI) will be presented. Tendon neovascularity, presence of spurs, calcification and/or tears in the common extensor tendon (lateral epicondyle) incidence will be analyzed using logistic regression and the OR including 95 % CI will be presented.

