#### Measurements

The primary outcome measures include self-perceived recovery measured using 6point Global Rating of Change (GROC) pain free grip strength pain (PFGS) and functionality. GROC measurement will contain a six point Likert scale describing the change from much worse to totally improved, PFGS will be measured with a Jamar hand dynamometer, pain with 0-10 scale (Numerical rated pain scale) and functional disability with the patient-rated tennis elbow (PRTEE) questionnaire. Secondary outcomes include: Tendon thickness, neovascularity, presence of spurs, calcification and/or tears in the common extensor tendon (lateral epicondyle) measured with diagnostic ultrasound imaging. Also, isometric strength measurements of elbow flexors and extensors will be included using the BioFet force evaluation system (mean of three efforts of the maximum isometric contraction). All measurements will be taken at baseline, 6- and 12-weeks followup.

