## STATISTICAL ANALYSIS PLAN (SAP)

#### **Demographic and Baseline Characteristics**

All randomized participants will be included in statistical analysis. The following demographic and baseline characteristics will be summarized and statistically analyzed: gender, age, height and weight, smoking habits, type of work, physical activity level, previous episodes of LET, time course of condition, severity of pain, disability scores (PRTEE), pain free grip strength, isometric strength test of elbow flexors and extensors.

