## Primary outcomes

The primary analysis will compare the two interventions on their mean change in PFGS, PRTEE scores, pain reduction. The estimated difference in mean change

from baseline to 6 and 12 weeks and the corresponding 95 % confidence interval (CI) will be presented. We will estimate all continuous outcome measures by using baseline values as covariates in linear mixed models. For GROC logistic regression will be used and the odds ratio (OR) including 95 % Confidence Intervals (CI) will be presented.

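### The binary ultrasound outcomes have no baseline term in their logistic models, and the plan does not say whether the event is presence at follow-up or a new finding

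*Protocol*

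**What the plan says.** The Measurements section lists the secondary imaging outcomes as "Tendon thickness, neovascularity, presence of spurs, calcification and/or tears in the common extensor tendon (lateral epicondyle) measured with diagnostic ultrasound imaging" and sets the schedule: "All measurements will be taken at baseline, 6- and 12-weeks followup". A baseline reading of each binary finding is therefore collected.

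The Primary outcomes section gives the only rule on baseline adjustment, and it is limited by type of variable: "We will estimate all continuous outcome measures by using baseline values as covariates in linear mixed models".

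The Secondary Outcomes section treats tendon thickness and isometric strength as "the difference in mean change from baseline to 6 and 12 weeks". For the binary findings it says "Tendon neovascularity, presence of spurs, calcification and/or tears in the common extensor tendon (lateral epicondyle) incidence will be analyzed using logistic regression", reported as an odds ratio with a 95% confidence interval. No baseline term, at-risk set or visit is named.

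The list under Demographic and Baseline Characteristics ends with "severity of pain, disability scores (PRTEE), pain free grip strength, isometric strength test of elbow flexors and extensors" and contains no ultrasound finding.

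**The concern.** Presence at follow-up and incidence are different quantities. Presence includes patients who already had the finding at entry. Incidence counts only patients who acquire it. The sentence uses both words and chooses neither, and the baseline scan has no stated role under either reading.

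- **If presence is meant**, a chance difference between arms at entry passes into the treatment odds ratio to the extent that findings persist. The plan also forgoes a covariate that is already measured and is likely to predict the outcome.
- **If new findings are meant**, patients positive at baseline leave the analysis. Resolution, one way in which a treatment could help, then cannot be observed, and the number at risk may be very small.

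Because ultrasound is absent from the baseline summary, a reader of the results might not see an imbalance at all.

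**Working it through.** **The plan's own figure.** The only calculation in the protocol is for pain-free grip strength (difference 7 kg, SD 7.1 kg, alpha 0.05, power 80%). It reproduces: 2 × (7.1 × (1.960 + 0.842) / 7)² = 16.15 per group. Then 16.15 / 0.9 = 17.94, so 18 per group and 36 in total. No rate or power is stated for the ultrasound outcomes. I use 18 per arm. The Sample section gives 42 patients, or 21 per arm, and I show that where it matters.

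**Assumptions (none is in the documents).** Baseline prevalence p, persistence s and new-onset rate i, varied as shown.

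**1. Chance imbalance at entry.** With two independent binomial counts of size 18 and the same p, the probability that they differ by 4 or more is:

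| p | Probability |
|---|---|
| 30% | 20% |
| 50% | 24% |
| 60% | 23% |

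If every finding persisted and none appeared, a split of 11/18 against 7/18 would give OR = (11 × 11) / (7 × 7) = 2.47, with two-sided p about 0.18 (Fisher 0.32).

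**2. Presence and new onset give different odds ratios.** Follow-up prevalence per arm = p·s + (1 − p)·i. Take s = 1 and new onset 5% against 15%.
- New-onset OR = (0.05/0.95) / (0.15/0.85) = 0.30.
- At p = 30%, presence is 0.30 + 0.70 × 0.05 = 0.335 against 0.30 + 0.70 × 0.15 = 0.405. OR = (0.335/0.665) / (0.405/0.595) = 0.74.
- At p = 10% and 50% the presence OR is 0.55 and 0.82.

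**3. New findings only.** Expected at risk per arm = 18 × (1 − p), which is 16.2, 12.6 and 9.0 at p = 10%, 30% and 50%. At 5% against 15%, expected new cases run from 0.5 to 2.4 per arm. The chance that at least one arm has no event is 1 − [1 − (1 − 0.05(1 − p))^18] × [1 − (1 − 0.15(1 − p))^18] = 48%, 59% and 72%. Ordinary logistic regression then has no finite odds ratio.

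**4. Gain from the baseline covariate.** Illustration with 18 per arm, baseline prevalence 60%, new findings 3%, and a penalised likelihood-ratio test (simulation; the range is across runs):

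| Resolution by arm | Power without baseline | Power with baseline |
|---|---|---|
| 15% against 60% | 40-42% | 52-56% |
| 15% against 50% | 28% | 36% |

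With no treatment effect, rejection was about 6-7% without baseline and 2-3% with it, so the adjusted test gained power while being the more conservative.

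**5. Empty cells.** In the first scenario of step 4, follow-up prevalence is 0.60 × 0.85 + 0.40 × 0.03 = 52.2% against 0.60 × 0.40 + 0.40 × 0.03 = 25.2%. The unadjusted two-by-two table then has an empty cell in 0.5% of trials (0.2% at 21 per arm). For rare findings the figure rises: about 28% at 10% prevalence in both arms, and 43% at 5% against 15% (36% at 21 per arm). In the adjusted model, no baseline-negative patient turns positive with probability (1 − 0.40 × 0.03)^36 = 0.988^36 = 65%, which makes the baseline coefficient infinite under ordinary maximum likelihood.

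**The case against.** A reader might infer that the plan counts pre-existing spurs, calcification or tears as outcome events. It does not say so. Read literally, incidence means new findings and would exclude patients positive at entry. The defect is an undefined event, not a stated wrong one.

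A reader might also infer bias. Randomisation keeps the expected odds ratio at 1 when there is no effect, and ordinary chance imbalance is already reflected in the planned confidence interval: the 11 against 7 split above is far from significance. What is lost is precision and protection against the imbalance of the one trial that is run.

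Nor do the documents support a premise that most findings are present at entry and rarely change. No prevalence or persistence is given, entry requires no ultrasound abnormality, and the power illustration itself assumes substantial resolution. Infinite odds ratios in the unadjusted model are frequent only for rare findings. In the first power scenario, separation arises mainly from adding the covariate.

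Finally, covariates and sparse-data rules are often left to a separate SAP. That has some force. However, the protocol's own section headed as the statistical analysis plan names the model, the effect measure and a baseline rule limited to continuous outcomes. As written, the binary models have no baseline term.

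**Conclusion.** The point holds as a correctable weakness in the secondary analysis. The protocol collects the baseline finding, gives it no role in the binary models, and leaves the event undefined between two quantities. Each reading has a cost: uncorrected chance imbalance and lower precision under presence, or loss of resolution and very few patients at risk under new onset.

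Under the assumed rates, the power gain from adding baseline status is roughly 8 to 14 percentage points. These sizes rest on assumed prevalence, onset and resolution and on 18 per arm. They illustrate direction and order of magnitude only. The primary outcomes are unaffected.

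**What to change.** In the Secondary Outcomes section:

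- Define each binary ultrasound outcome as presence of the finding at 6 weeks and at 12 weeks.
- Include the baseline finding (present/absent) as a covariate in each logistic model.
- Report the baseline-to-follow-up change table by arm (present or absent at entry against present or absent at each visit).
- Keep the term incidence for patients free of the finding at baseline.
- Because the adjusted model can meet empty cells at this sample size, specify penalised (Firth) or exact logistic regression, or report counts only when few patients change status.

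No new data are needed, since the baseline scans are already scheduled. The cost is plan wording and, for penalised or exact regression, possibly software beyond the standard menus of SPSS 25, which the Data Analysis section names for all analyses. That sentence would then need a matching exception.

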#### SUBJECTS CONFIDENTIALITY AND ETHICAL CONSIDERATIONS

In order to maintain subject confidentiality, only a site number, subject number and subject initials will identify all study subjects. Data will be kept safe using records with coded numbers. All study records will be kept in a locked file cabinet and code sheets linking a patient's name to a patient identification number will be stored separately in another locked file cabinet. The study will be conducted according to the Declaration of Helsinki, Protection of Human Volunteers. Patients will participate voluntarily, will be free to withdraw at any time and, sign a consent form prior entering the study.

